14. Unwilling to limit alcohol consumption to within moderate limits for the duration of the study, as follows: not more than 14 units per week for women and 21 units per week for men (1 Unit = 150 mL of wine, 360 mL of beer, or 45 mL of 40% alcohol)
15. Use of illicit drugs (such as cocaine, phencyclidine [PCP]) within 1 year prior to the Screening visit or positive urine drug screen at Screening (a urine drug screen deemed

positive due to prescription medications or for benzodiazepines, opioids or marijuana is acceptable and inclusion is at the discretion of the PI)

16. Use of an investigational agent or device within 30 days prior to first dose or current participation in an investigational study
17. Blood donation (500 mL) within 7 days prior to first dose. Donation or loss of whole blood (excluding the volume of blood that will be drawn during the Screening procedures of this study) prior to administration of the study treatment as follows: 50 mL to 499 mL of whole blood within 30 days, or more than 499 mL of whole blood within 56 days prior to study treatment administration
18. Any concomitant medical or psychiatric condition or social situation that would make it difficult to comply with protocol requirements or put the participant at additional safety risk
19. Participants who are unable to return for all scheduled study visits
20. For NHV cohorts only, ALT or AST > ULN at Screening
21. Serum sodium < LLN or serum potassium > ULN at Screening
22. eGFR of < 60 mL/min/m², at Screening
23. Platelet count < LLN at Screening (NHVs only)

Additional Exclusion Criteria for CF Patients

A potential participant will be excluded from the study if any of the following criteria apply:

1. CF exacerbation within **30 days** of first dose
2. History of solid organ transplant
3. ALT or AST > **2.5 X ULN** at Screening
4. Platelet count < 100,000 at Screening
5. Diagnosis of hepatic cirrhosis based on medical history and documented in medical record or other source document.

Notes:

- Sponsor Medical Monitor has the option to exclude the enrollment of a participant if, based upon the participant's medical history or Screening results, it is felt that a participant's safety may be at risk and/or if the safety data may confound or conflict with the study results.
- All spirometry tests used as inclusion criteria and all laboratory tests used as exclusion criteria may be repeated once during Screening, with the repeat value used for inclusion/exclusion purposes.

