## 5. DEFINITIONS

### Study Day:

Day of study relative to the date of first dose of active drug or placebo. First dose date will be considered as Day 1. Calculated prior to first dose date as (date of measurement – date of first dose) and calculated after first dose date as (date of measurement – date of first dose + 1).

Baseline:

The last observation prior to the first dose of active drug or placebo. The baseline value may be an unscheduled or repeated measurement.

Change (absolute) from baseline:

The arithmetic difference between a post-baseline value and baseline for a given time point: change (absolute) from baseline = (post-dose value – baseline value).

Percent change from baseline:

The percent change between a post-baseline value and baseline for a given time point: [(post-dose value – baseline value) / baseline value] \*100%

Treatment-emergent AEs (TEAEs):

TEAE will be derived as any AEs occurring on or after the first dose.

Treatment-emergent SAEs (TESAEs):

TESAE will be derived as any serious AEs occurring on or after the first dose.

Concomitant Medications:

Concomitant medications will be derived as any medications with an end date on or after the first dose.

Use of medications at baseline:

For each of the following medications: CFTR modulators, inhaled hypertonic saline, inhaled bronchodilators, chronic inhaled antibiotics, inhaled corticosteroids, dornase alfa, and azithromycin, any use within 30 days prior to first dose will be considered as use at baseline. Dornase alfa and azithromycin will be identified by the Preferred Drug Name as coded by WHODrug. All other medications will be identified as recorded on the CF-Concomitant Medications eCRF.

Sputum pseudomonas status at baseline:

Any pseudomonas (as collected on the Airway Infection eCRF) present within 30 days prior to first dose will be considered as positive at baseline.

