### **9.5.2      Laboratory Test Results**

Laboratory assessments include clinical chemistry, coagulation, hematology, urinalysis, and urine electrolytes. Microscopic urinalysis will also be performed as needed, with results listed by subject but not otherwise summarized. Clinical laboratory values will be expressed using the International System of Units (SI).

Descriptive statistics summaries of quantitative laboratory tests will be provided by scheduled visit. Derived changes and percent changes from baseline to each scheduled postdose visit will be included. Additionally, descriptive statistics for the peak post-baseline values will be included for the chemistry lab tests: ALT, AST, ALP, and BILI, and descriptive statistics for the lowest post-baseline values and lowest overall values will be provided for the hematology lab tests: HGB and PLT. Laboratory test values above or below the limits of detection will be set to the upper or lower limit values, respectively, for inclusion in the descriptive statistics summaries; values will be reported without imputation in the listings.

Plots of mean (+/- SD) key laboratory test results over time will be provided by study day. The key laboratory tests to be included will be: alanine aminotransferase, aspartate aminotransferase, total bilirubin, creatine kinase, creatinine, potassium, and sodium. SD bars below 0 will be set to 0.

Scatter plots of peak post-baseline total bilirubin [divided by upper limit of normal (ULN)] vs peak post-baseline alanine aminotransferase [divided by ULN] will be provided to visually evaluate drug-induced serious hepatotoxicity.

---

Additionally, select laboratory tests from serum chemistry, coagulation, and hematology will be programmatically graded using the National Cancer Institute (NCI) Common Terminology Criteria for Adverse Events (CTCAE) version 5.0 grading criteria (Appendix A). Laboratory test values above or below the limits of detection will be set to the upper or lower limit values, respectively, for programmatic grading. Using the CTCAE grades, shift tables describing changes from baseline to the maximum post-baseline grade will be provided for clinical chemistry, coagulation, and hematology laboratory results. The number and percent of subjects will be reported in each shift category. Assessments which are missing a baseline value or which are not graded at baseline will be summarized as unknown.

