Aspartate aminotransferase, increased	Normal baseline: > ULN – 3.0 x ULN Abnormal baseline: 1.5 x – 3.0 x baseline	Normal baseline: > 3.0 x – 5.0 x ULN Abnormal baseline: > 3.0 x – 5.0 x baseline	Normal baseline: > 5.0 x – 20.0 x ULN Abnormal baseline: > 5.0 x – 20.0 x baseline	Normal baseline: > 20.0 x ULN Abnormal baseline: > 20.0 x baseline
Bicarbonate, decreased	< LLN and no intervention initiated			

	Grade 1	Grade 2	Grade 3	Grade 4
Calcium (corrected), high (Hypercalcemia)	> ULN – 2.9 mmol/L	> 2.9 – 3.1 mmol/L or symptomatic	> 3.1 – 3.4 mmol/L or hospitalization indicated	> 3.4 mmol/L or life-threatening consequences
Calcium (corrected), low (Hypocalcemia)	< LLN – 2.0 mmol/L	< 2.0 – 1.75 mmol/L or symptomatic	< 1.75 – 1.5 mmol/L or hospitalization indicated	< 1.5 mmol/L or life-threatening consequences
Creatinine, increased	> ULN – 1.5 x ULN	Normal baseline: > 1.5 – 3.0 x ULN Abnormal baseline: > 1.5 x – 3.0 x baseline	> 3.0 – 6.0 x ULN OR > 3.0 x baseline	> 6.0 x ULN
Creatine phosphokinase, increased	> ULN – 2.5 x ULN	> 2.5 – 5.0 x ULN	> 5 – 10 x ULN	> 10 x ULN
Gamma glutamyl transferase, increased	Normal baseline: > ULN – 2.5 x ULN Abnormal baseline: 2.0 x – 2.5 x baseline	Normal baseline: > 2.5 x – 5.0 x ULN Abnormal baseline: > 2.5 x – 5.0 x baseline	Normal baseline: > 5.0 x – 20.0 x ULN Abnormal baseline: > 5.0 x – 20.0 x baseline	Normal baseline: > 20.0 x ULN Abnormal baseline: > 20.0 x baseline
Glucose, high (Hyperglycemia)	Abnormal glucose above baseline with no medical intervention	Change in daily management from baseline for a diabetic or oral antiglycemic agent initiated or workup for diabetes	Insulin therapy initiated or hospitalization indicated	Life-threatening consequences or urgent intervention indicated
Glucose, low (Hypoglycemia)	< LLN - 3.0 mmol/L	< 3.0 - 2.2 mmol/L	< 2.2 - 1.7 mmol/L	< 1.7 mmol/L or life-threatening consequences or seizures
Potassium, high (Hyperkalemia)	> ULN – 5.5 mmol/L	> 5.5 – 6.0 mmol/L or intervention indicated	> 6.0 – 7.0 mmol/L or hospitalization indicated	> 7.0 mmol/L or life-threatening consequences
Potassium, low (Hypokalemia)	< LLN – 3.0 mmol/L without symptoms	< LLN – 3.0 mmol/L with symptoms or intervention indicated	< 3.0 – 2.5 mmol/L or hospitalization indicated	< 2.5 mmol/L or life-threatening consequences

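### Creatinine grading in SAP Appendix A leaves a band of values with no grade when baseline exceeds the ULN, so the shift table can understate worsening

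*SAP*

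**What the plan says.** SAP Section 9.5.2 says that "select laboratory tests from serum chemistry, coagulation, and hematology will be programmatically graded" with the criteria in Appendix A (Section 13), and that "shift tables describing changes from baseline to the maximum post-baseline grade will be provided".

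The creatinine row of Appendix A has four cells:

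- Grade 1: above ULN and up to 1.5 times ULN, with no reference to baseline.
- Grade 2: "Normal baseline: > 1.5 – 3.0 x ULN Abnormal baseline: > 1.5 x – 3.0 x baseline".
- Grade 3: "> 3.0 – 6.0 x ULN OR > 3.0 x baseline", with no condition on baseline.
- Grade 4: above 6.0 times ULN.

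The only rule in Section 9.5.2 for values without a grade concerns baseline: "Assessments which are missing a baseline value or which are not graded at baseline will be summarized as unknown". It says nothing about a post-baseline value that meets no grade, or about a value that meets two. SAP Section 5 defines baseline as "The last observation prior to the first dose of active drug or placebo". The SAP does not define an abnormal baseline.

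**The concern.** For a subject whose baseline is above ULN, Grade 1 ends on one scale (ULN) and Grade 2 begins on another (baseline). Nothing makes the two cut-offs coincide. Between them, a creatinine value that has risen loses the grade that a lower value would have had. An ordinal scale should not do that, and a program that applies the printed rules will not correct it.

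The appendix suggests that this is a drafting slip. ALT, AST, alkaline phosphatase, GGT and total bilirubin also distinguish normal from abnormal baselines, but they do so from Grade 1 upward, so their Grade 1 and Grade 2 bands join. Creatinine is the only one of these rows that introduces the split at Grade 2.

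What is at stake is the creatinine shift table. Creatinine is one of seven key laboratory tests in Section 9.5.2. The protocol discusses renal ENaC inhibition as a class concern (Sections 5.2.2 and 5.7), so readers will look at renal results.

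**Working it through.** The plan states no figure on this point, so there is none to reproduce. The check applies the printed cells.

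**Notation.** b = baseline / ULN and x = post-baseline value / ULN. Take abnormal to mean b > 1. All inputs are from the creatinine row of SAP Appendix A.

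**Rules for b > 1**

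- Grade 1: 1.0 < x ≤ 1.5
- Grade 2: 1.5b < x ≤ 3.0b
- Grade 3: 3.0 < x ≤ 6.0, or x > 3.0b
- Grade 4: x > 6.0

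**Gap.** Grade 1 stops at x = 1.5. Grade 2 starts above 1.5b, which exceeds 1.5 whenever b > 1. Above x = 3.0 the ULN part of Grade 3 applies at any baseline. The ungraded band is therefore 1.5 < x ≤ min(1.5b, 3.0).

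| Baseline b | Ungraded x | Change from baseline across the band |
|---|---|---|
| 1.1 | 1.5 to 1.65 | +36% to +50% |
| 1.2 | 1.5 to 1.80 | +25% to +50% |
| 1.3 | 1.5 to 1.95 | +15% to +50% |
| 1.5 | 1.5 to 2.25 | 0% to +50% |
| 2.0 | 1.5 to 3.0 | −25% to +50% |

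The lower change is 1.5/b − 1 (for b = 1.2, 1.5/1.2 = 1.25). The upper change is 1.5b/b − 1 = 50%.

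**Effect on the shift table at b = 1.2 (Grade 1 at baseline)**

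| Post-baseline x | Maximum grade as printed | Reads as |
|---|---|---|
| 1.7, 1.7, 1.7 | none | 1 to 0 if no grade is coded 0, despite a 42% rise (1.7/1.2 = 1.42) |
| 1.7, 1.75, 0.95 | none | 1 to 0 on the same coding |
| 1.3, 1.7, 1.4 | 1 | no change |
| 1.9, 1.7, 1.7 | 2 | worsening |

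A false improvement therefore needs three things: a baseline above 1.0 and up to 1.5 times ULN; every post-baseline value either in the gap or at or below ULN; and no grade tabulated as Grade 0. The third row is the milder result: a single value in the Grade 1 band turns a false improvement into no change, and the rise to 1.7 goes uncounted.

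**Baseline itself in the gap.** If b is above 1.5 and up to 3.0, then b lies within 1.5 < x ≤ min(1.5b, 3.0). The baseline has no grade, and the subject goes to the unknown category.

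**The case against.** **Exposure is small, and the data are not lost.** Protocol Section 8.3 excludes "eGFR of < 60 mL/min/m², at Screening". Section 8.2 limits age to 18–55 years and excludes findings of clinical relevance other than CF, and Section 10.3.6 excludes clinically significant laboratory abnormalities confirmed on repeat. Shift tables use the maximum grade over many visits: Table 1.4 schedules clinical laboratory tests at all twelve visits after Day 1 in Cohort 6, so one ordinary Grade 1 value removes the false improvement. No formal testing is planned, creatinine is not in the stopping rules, and AE reporting rests on investigator judgement. Creatinine is also summarised by visit with changes from baseline, plotted over time, and listed with reference ranges and flags. All of this stands and keeps the point minor. It does not remove the gap: there is no creatinine entry limit, baseline can differ from Screening, and no other SAP text assigns a grade to these values.

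**Stronger readings that a reader might infer.**

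- *Renal shift tables generally show worsening as improvement.* They do not. Only the abnormal-baseline gap can do this, under the three conditions above, and the SAP does not state the third.
- *Grade 2 is lost when baseline is at or below half the ULN.* There 3.0b ≤ 1.5, so every value above 1.5 times ULN also meets the baseline part of the Grade 3 cell. That cell grades a more than threefold rise as 3 for everyone, as written. Losing Grade 2 also depends on a highest-grade rule that the SAP does not state. The effect is a higher grade, not a missing one.
- *Normal and abnormal baselines are treated inconsistently, since a large fold-rise within low values may earn less than a smaller rise from a raised baseline.* This is the appendix's convention for the liver tests as well. Preferring another is a matter of judgement, not an error.

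**Conclusion.** The gap is real as printed: with baseline above ULN, values above 1.5 times ULN and up to 1.5 times baseline, capped at 3.0 times ULN, have no grade. The error is minor. It is confined to one row of one set of shift tables and probably touches few subjects; the documents give no count of subjects with raised baseline creatinine. The arithmetic rests on reading abnormal baseline as above ULN. The false improvement also rests on an ungraded post-baseline value being coded as Grade 0. That coding is plausible, since normal values also meet no grade, but the SAP does not specify it.

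**What to change.** In the creatinine Grade 2 cell, change the abnormal-baseline criterion to: above 1.5 and up to 3.0 times ULN, OR above 1.5 and up to 3.0 times baseline. Add one sentence to Section 9.5.2 saying that the highest grade met is assigned, and that abnormal here means above ULN.

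For b > 1 this gives Grade 1 up to 1.5 times ULN, Grade 2 up to 3.0 and Grade 3 above that, with no hole. All four examples above then have a maximum of Grade 2, and a baseline above 1.5 and up to 3.0 times ULN is graded 2 instead of unknown. With the highest-grade sentence in place, the ULN part does all the work when b > 1. The normal-baseline Grade 1 and Grade 2 criteria stay as they are; the sentence only settles values that meet two grades.

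The OR should not be extended to all subjects. With 1.5b ≤ 1.0, that is b at or below 0.667, Grade 1 would become unreachable and Grade 2 would start at or below ULN (at b = 0.6, from above 0.9 times ULN). Copying the bilirubin pattern would join the bands, but a raised baseline would then have no grade itself, because it is not above 1.0 times baseline.

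The cost is one cell and one sentence before database lock, and a few more Grade 2 flags in subjects with raised baseline creatinine.

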6.2. Secondary Endpoints

1. Changes from pre-dose baseline in serum electrolytes in NHVs and CF patients as a safety measure.
2. Changes from pre-dose baseline in Forced Expiratory Volume (FEV1) in NHVs as a measure of safety.

3. Pharmacokinetics of ARO-ENaC in NHVs and in CF patients

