Sodium, high (Hypernatremia)	> ULN – 150 mmol/L	> 150 - 155 mmol/L or intervention initiated	> 155 – 160 mmol/L or hospitalization indicated	> 160 mmol/L or life-threatening consequences
Sodium, low (Hyponatremia)	< LLN – 130 mmol/L	125-129 mmol/L without symptoms OR 120-124 mmol/L regardless of symptoms	125-129 mmol/L with symptoms OR 120-124 mmol/L regardless of symptoms	< 120 mmol/L or life-threatening consequences
Total bilirubin, increased	Normal baseline: > ULN – 1.5 x ULN Abnormal baseline: > 1.0 x – 1.5 x baseline	Normal baseline: > 1.5 x – 3.0 x ULN Abnormal baseline: > 1.5 x – 3.0 x baseline	Normal baseline: > 3.0 x – 10.0 x ULN Abnormal baseline: > 3.0 x – 10.0 x baseline	Normal baseline: > 10.0 x ULN Abnormal baseline: > 10.0 x baseline
Coagulation				

	Grade 1	Grade 2	Grade 3	Grade 4
INR, increased	Not on anticoagulant: > 1.2 – 1.5 On anticoagulant: > 1.0 x – 1.5 x baseline OR monitoring indicated	Not on anticoagulant: > 1.5 – 2.5 On anticoagulant: > 1.5 x – 2.5 x baseline OR dose adjustment indicated	Not on anticoagulant: > 2.5 On anticoagulant: > 2.5 x baseline OR bleeding	
Activated Partial Thromboplastin Time, prolonged	> ULN – 1.5 x ULN	> 1.5 x – 2.5 x ULN	> 2.5 x ULN or bleeding	

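### SAP Appendix A lists sodium of 120-124 mmol/L under both Grade 2 and Grade 3, leaving the programmed grade undefined; the effect is confined to the sodium grade and its shift table

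*SAP*

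**What the plan says.** SAP Section 9.5.2 states that "select laboratory tests from serum chemistry, coagulation, and hematology will be programmatically graded using the National Cancer Institute (NCI) Common Terminology Criteria" version 5.0, as set out in Appendix A. The stated use of the grades is a table: "shift tables describing changes from baseline to the maximum post-baseline grade will be provided for clinical chemistry, coagulation, and hematology laboratory results".

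In Appendix A, the low-sodium row has these cells:

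- Grade 1: from below the lower limit of normal (LLN) down to 130 mmol/L.
- Grade 2: "125-129 mmol/L without symptoms OR 120-124 mmol/L regardless of symptoms".
- Grade 3: "125-129 mmol/L with symptoms OR 120-124 mmol/L regardless of symptoms".
- Grade 4: "< 120 mmol/L or life-threatening consequences".

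Protocol Section 6.2 lists as a secondary endpoint "Changes from pre-dose baseline in serum electrolytes in NHVs and CF patients as a safety measure". SAP Section 9.5.2 also names the tests whose means are plotted over time: "alanine aminotransferase, aspartate aminotransferase, total bilirubin, creatine kinase, creatinine, potassium, and sodium". Protocol Section 8.3 excludes anyone whose serum sodium is below the LLN at Screening.

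**The concern.** The first alternatives in the Grade 2 and Grade 3 cells differ properly: one is for patients without symptoms, the other for patients with them. The second alternative is the same in both cells and applies whatever the symptoms. A sodium of 122 mmol/L therefore satisfies both definitions. A program that tests Grade 2 first returns 2, and one that tests Grade 3 first returns 3. Both would follow the SAP.

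Because the cells differ in their first alternative, this does not look like one cell extracted twice from the PDF.

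At stake is the sodium row of the shift table, in a trial of a drug that acts on a sodium channel and names electrolyte disturbance as a risk (Protocol Section 5.7). A low value could be tabulated one grade below where the rest of the row implies it belongs. If the gap is noticed only when such a value occurs, the choice is made with data in hand. SAP Section 7 allows unblinded outputs before the final analysis.

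**Working it through.** The plan gives no figure to reproduce. The check is to treat the row as a set of rules and see which grades each value meets.

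**Inputs.** The four cells of the low-sodium row in SAP Appendix A. An LLN of 135 mmol/L is assumed because the documents give none; it moves only the upper edge of Grade 1.

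**Step 1. The row as written**, applied to whole-number values from 118 to 134 mmol/L:

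| Sodium (mmol/L) | Grades met, no symptoms | Grades met, symptoms |
|---|---|---|
| 130-134 | 1 | 1 |
| 125-129 | 2 | 3 |
| 120-124 | 2 and 3 | 2 and 3 |
| 118-119 | 4 | 4 |

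Five whole-number values (120, 121, 122, 123, 124) meet two grades. Knowing the symptoms does not help, since both cells disregard them in this range.

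**Step 2. Is there a tie-break?** The shift-table rule takes the highest grade after baseline. That chooses among a subject's assessments once each has a grade. It does not say which grade a single assessment receives, and it does not apply to the baseline grade. Neither document has another rule.

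**Step 3. Which cell should keep the range?** Read the grades in order as sodium falls through 125-129, 120-124 and below 120:

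| 120-124 kept in | No symptoms | Symptoms |
|---|---|---|
| Grade 2 only | 2, 2, 4 | 3, 2, 4 |
| Grade 3 only | 2, 3, 4 | 3, 3, 4 |

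With the range in Grade 2 only, a symptomatic patient at 122 is graded lower than a symptomatic patient at 127. With it in Grade 3 only, the grade never falls as sodium falls. Every whole-number value then meets exactly one grade for a given symptom status, and the overlap goes from five values to none.

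**Step 4. Size.** The ambiguity is 3 - 2 = 1 grade. One affected subject, as a share of the planned active group (Protocol Table 4), is:

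- Cohorts 1-4, 2b and 3b: 1/4 = 25%
- Cohort 5: 1/8 = 12.5%
- Cohort 4b: 1/9 = 11.1%
- Cohort 6: 1/18 = 5.6%

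SAP Section 9 groups subjects by dose and regimen. If Cohorts 4 and 5 receive the same dose, their group is 4 + 8 = 12 and the share is 1/12 = 8.3%. The documents give no expected frequency for sodium of 120-124, so no expected number of affected subjects can be computed.

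**The case against.** The best reply is that little depends on this. The shift table already takes the maximum post-baseline grade, so a programmer would naturally choose 3. A baseline value in this range is unlikely given the Screening exclusion. SAP Section 8.5 requires independent validation programming, which could expose the conflict. The raw value would still appear in the minimum of the descriptive statistics and in both laboratory listings. Adverse event severity is the investigator's judgment (Protocol Section 11.5.1) and is not derived from Appendix A. The stopping rules in Protocol Section 7.4 use neither sodium nor a CTCAE grade.

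Most of this stands and limits the consequence. It does not remove the defect. Choosing 3 is an inference that the SAP does not state. Independent programming may reveal a disagreement, but the SAP gives no text to resolve it. Baseline is the last pre-dose observation (SAP Section 5), not the Screening value, so the exclusion makes a low baseline rare but not impossible.

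Three stronger readings are tempting, and the documents do not support them:

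- **That the secondary endpoint is compromised.** The endpoint is a change from baseline. SAP Section 9.5.2 summarises it from the measured values, and no grade enters it.
- **That the error crosses a moderate/severe boundary.** Appendix A uses grade numbers only, and neither document maps Grades 2 and 3 to those words.
- **That all values of 125-129 should be Grade 2 because a laboratory program cannot see symptoms.** This would move symptomatic patients out of Grade 3, where the table puts them, and so create under-grading. Symptom or intervention qualifiers also occur in other rows, such as amylase, calcium and potassium. How the program obtains them is a general question, not a reason to rewrite this row.

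**Conclusion.** The point holds in a limited form. The low-sodium row is contradictory as written: sodium of 120-124 mmol/L has two grades, one apart, and the SAP does not choose between them. The effect is confined to the CTCAE grade for sodium and the sodium shift table.

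The figure of 25% for one subject is the worst case and applies only to groups of four. That affected values will be rare is a judgment based on the Screening exclusion, not a computed rate. That Grade 3 is the right home for the range rests on the row's own ordering: symptomatic 125-129 is already Grade 3.

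The correction is worth making because an executable rule is wrong on its face and the repair is trivial. It should not be presented as a threat to the trial's endpoints or to participant safety.

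**What to change.** In SAP Appendix A, low-sodium row, delete the second alternative (the 120-124 range) from the Grade 2 cell and leave the Grade 3 cell as it is. Check the corrected row against the CTCAE version 5.0 source that the SAP names. Keep the symptom split for 125-129 unchanged, and do not add a rule that makes all values in that range Grade 2.

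The cost is one clause in one table cell, with no effect on data collection, sample size or conduct. Make the change before database lock, and before any further unblinded laboratory tables are produced, so that the choice cannot depend on whose value is affected. If any sodium grades have already been programmed, check how 120-124 was coded.
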